12.4 Collection and Recording of Adverse Events

12.4.1 Collection Period

Adverse Events temporally associated (24 hours) with the research blood draws and nasal swabs will be collected from the time of the screening visit until a subject completes study participation.

COVID-19 Vaccine Dose Alone: Adverse Events as defined in Section 12.2.1 will be collected for 30 days following COVID-19 vaccine administration. Serious Adverse Events will be collected for 6 months following vaccine administration.

COVID-19 Vaccine Dose plus IS Reduction: All Adverse Events will be collected in those who undergo immunosuppression reduction occurring from the onset of IS reduction until 30 days after return to full immunosuppression. Serious Adverse Events will be collected for 6 months post onset of IS reduction.

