6.7 Immunosuppression Reduction

6.7.1 Immunosuppression (IS) Reduction

Participants on a tacrolimus-based regimen that includes MMF (or equivalent), with or without corticosteroid:

MMF (or equivalent) will be withheld for five days prior to and 2 weeks following vaccine administration. During the interval that MMF is withheld, no adjustments will be made to the CNI or corticosteroid dose.

Participants on a tacrolimus based regimen with a trough level ≥ 5 ng/mL, with or without ≤ 5 mg Prednisone (or equivalent) and no MMF or other antimetabolite

Reduce CNI by 25% of starting dose for 5 days prior to and 2 weeks following vaccine administration.

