12.2 Definitions

12.2.1 Adverse Event (AE)

Any untoward or unfavorable medical occurrence associated with the subject's participation in the research, whether or not considered related to the subject's participation in the research (modified from the definition of adverse events in the 1996 International Conference on Harmonization E-6 Guidelines for Good Clinical Practice) (from OHRP "Guidance on Reviewing and Reporting Unanticipated Problems Involving Risks to Subjects or Others and Adverse Events (1/15/07)" <http://www.hhs.gov/ohrp/policy/advevntguid.html#Q2>)

For this study, adverse events will be considered for association with the additional dose of COVID-19 vaccine and study mandated procedures as follows:

Vaccine Administration (Moderna COVID-19 Vaccine (monovalent, bivalent, and 2023-2024 formula as per protocol version), Pfizer-BioNTech COVID-19 Vaccine (monovalent, bivalent, and 2023-2024 formula as per protocol version)

All AEs occurring within 30 days following a single COVID-19 vaccine dose and SAEs up to 6 months post vaccine administration.

Study mandated procedures:

Any AE occurring within 24 hours of a protocol mandated blood draw
Any AE occurring within 24 hours of a protocol mandated nasal swab
Any AE occurring within 24 hours of an oral fluid collection
Any AE occurring during the period from the onset of immunosuppression reduction until 30 days after return to full immunosuppression and SAEs up to 6 months post return to full immunosuppression.

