13.4.3 Analyses of Secondary and Other Endpoint(s)/Outcome(s)

All binary secondary endpoints will be analyzed using a Fisher exact test. Severe adverse events will be analyzed by calculating the incidence rate difference with a two-sided 95% confidence interval for immunoreduction vs no immunoreduction participants.

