Appendix 3: Schedule of Events (IS Reduction plus COVID-19 Vaccine Dose)

Study Schedule	Days			Weeks						Months				
Time points	-5	0	3 ¹	1	2	3	4	5	6	3	6	9	12	For Cause ²
Visit #	01	02	03	04	05	06	07	08	09	10	11	12	13	FC
Visit Windows (+/-)	-	-	1d	1d	3d	3d	3d	3d	3d	2w	2w	2w	2w	-
General Assessments														
Study Contact ³	X	X		X	X	X	X	X	X	X	X		X	X
Medications (immunosuppression, PrEP, COVID-19 treatment)	X ⁴	→	→	→	→	→	→	→	→	X	X ⁵	X ⁵	X ⁵	X
Assessment of Events (AE, SAE, rejection, graft loss)	X	→	→	→	→	→	→	→	→	→	→	→	X	X
Clinical Laboratory Assessments														
Complete Blood Count with differential		X			X		X				X	X		X
Metabolic Panel ⁶		X								X	X			X
eGFR, serum creatinine (kidney)		X		X	X	X	X	X	X					
Hepatic Panel including direct bilirubin (liver)		X									X			
Quantitative Immunoglobulins		X									X			
SARS-CoV-2 PCR (nasal swab, clinical)		X ⁷					X			X	X	X	X	X
Investigational Intervention														
Immunosuppression Reduction	X	→	→	→	X ⁸									
COVID-19 mRNA Vaccine		X												
Central Laboratory Assessments														
SARS-CoV-2 PCR (nasal swab, research)		X					X			X	X		X	X
Oral fluid anti-N and anti-S immunoglobulin levels		X					X			X	X		X	X
Anti-SARS-CoV-2 S (Roche Elecsys [®])					X		X			X	X		X	X
Donor Specific Antibodies (kidney only)							X			X	X		X	
Antibody/Neutralization assays		X			X		X			X	X		X	X
Spike Protein (subset of sites)		X	X											
Proteomics		X	X ⁹				X							
Transcriptomics		X	X ⁸				X							
T and B Cell Assays		X			X		X			X	X		X	X

¹ May be a home draw. The spike protein will only be performed at a subset of clinical sites.² Unscheduled "for cause" visit for suspected rejection. Participants with confirmed COVID-19 will send in a nasal swab for research.³ Study contacts may be remote.⁴ Ensure the participant has not taken any medications since screening that would make them ineligible.⁵ Only PrEP and COVID-19 related treatment collected at these visits.⁶ Comprehensive metabolic panel at baseline, basic metabolic panel all other timepoints (see study definitions).⁷ If the Day 0 nasal swab is positive, IS reduction will be prematurely discontinued and participants will be followed until Day 30 for safety. This includes the Day 30 clinical labs, DSA and AE/SAE assessment. No further mechanistic blood will be collected.⁸ Participant will be informed to restart full IS the following day.⁹ These Day 3 assessments will only be collected on participants included in the Day 3 spike protein.

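### AE collection windows differ by arm and the reduction-arm SAE end dates conflict, while the planned *severe* AE rate difference states no window or denominator

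*Combined protocol and SAP*

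**What the plan says.** **AE collection.** Section 12.4.1 sets a different rule for each arm. For vaccine alone: "Adverse Events as defined in Section 12.2.1 will be collected for 30 days following COVID-19 vaccine administration". For the reduction arm, events are collected "occurring from the onset of IS reduction until 30 days after return to full immunosuppression". Section 6.7.1 fixes the length of reduction. In the mycophenolate regimen, "MMF (or equivalent) will be withheld for five days prior to and 2 weeks following vaccine administration". In the regimen without an antimetabolite, the calcineurin inhibitor is lowered "for 5 days prior to and 2 weeks following vaccine administration". A footnote to the Week 2 visit in Appendix 3 adds: "Participant will be informed to restart full IS the following day".

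**SAE collection in the reduction arm.** Section 12.4.1: "Serious Adverse Events will be collected for 6 months post onset of IS reduction". Section 12.2.1: "SAEs up to 6 months post return to full immunosuppression". For vaccine alone, both sections give six months from the vaccine.

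**Other collection rules.** Section 12.2.3 asks all participants, without regard to arm, to report events up to 30 days after vaccine. The event-assessment rows of Appendices 2 and 3 run to Month 12.

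**Analysis.** Section 13.4.3: "Severe adverse events will be analyzed by calculating the incidence rate difference with a two-sided 95% confidence interval", reduction against no reduction. It names no time window and does not say whether the denominator is person-time or participants. The secondary safety endpoint in Sections 3.3.1 and 13.2 is *serious* events in the 30 days after vaccine. Objective 2.3 asks for the incidence of AEs and SAEs and gives no window.

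**The concern.** When the arms are watched for different lengths of time, a comparison over everything collected mixes the effect of reduction with the effect of longer observation. Counts or proportions favour the arm watched for less time. Rates can favour the arm watched for longer, if events bunch early and are spread over extra quiet days. Section 13.4.3 leaves open which of these would be reported.

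The event set is also unclear. Severity is a CTCAE grade (Section 12.3.1); seriousness is an outcome-based definition (Section 12.2.7). As written, the one AE-specific analysis does not match the listed endpoint. Sites meanwhile have two incompatible SAE end dates for the reduction arm.

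At stake are the AE incidence objective, the *severe* event contrast, and the DSMB's reading of its planned reviews, which under Section 12.7.2.1 include at least a listing of all reported AEs and SAEs.

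**Working it through.** The plan states no expected AE rate, so there is no figure of its own to reproduce. All event rates below are assumptions.

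**1. AE window.** Inputs: 5 days before and 14 days after vaccine (Section 6.7.1), plus 30 days after return (Section 12.4.1).
- Reduction arm: 5 + 14 + 30 = 49 days, Day -5 to Day 44 (50 days if counted from restart on the day after the Week 2 visit).
- Control: 30 days. Ratio 49/30 = 1.63 (50/30 = 1.67).
- Early return to baseline immunosuppression under Section 6.12 shortens the 49 days, so the window also depends on graft function.

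**2. SAE end date.** Six months taken as 6 × 30.44 = 182.6 days.
- Control: about Day 183.
- Reduction arm, Section 12.4.1: -5 + 182.6, about Day 178.
- Reduction arm, Section 12.2.1: 14 + 182.6, about Day 197.
- The two differ by 5 + 14 = 19 days. Under 12.4.1 the length equals control (183 days) but ends 5 days earlier relative to vaccine. Under 12.2.1 it is about 202 days, 10% longer than control.

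**3. Participants with an event, full windows, no true difference.** With the same constant hazard in both arms, p49 = 1 - (1 - p30)^(49/30). False-positive rates are for a two-sided Fisher exact test at 0.05 with 200 per arm (Section 13.7), by exact enumeration.

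| Control, 30 days (assumed) | Reduction, 49 days | False-positive rate |
|---|---|---|
| 2% | 3.2% | 6% |
| 5% | 8.0% | 18% |
| 10% | 15.8% | 36% |
| 20% | 30.5% | 64% |
| 30% | 44.2% | 81% |

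With 30 days in both arms, the same test gives 1.7% to 3.9% over these control rates.

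**4. Person-time rates, no true difference.**
- Constant hazard: numerator and denominator both scale by 49/30, so the bias is zero.
- Early clustering, assumed 1.0 event per participant in the first week plus 0.1 per 30 days of background: control (1.0 + 0.1)/30 = 3.67 per 100 person-days; reduction (1.0 + 0.1 × 49/30)/49 = 2.37; ratio 0.65.
- Early clustering, assumed 0.5 and 0.2: control 0.7/30 = 2.33; reduction (0.5 + 0.2 × 49/30)/49 = 1.69; ratio 0.72.
- Limiting case, every event soon after vaccine: 30/49 = 0.61.

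**5. Which outcomes depend on these windows.** From Sections 3.3.1, 12.2.2 and 13.2: SAEs 30 days; rejection, graft loss and death 60 days; dnDSA 90 days; solicited reactogenicity Day 7. All are anchored on the vaccine and the same in both arms. Only the AE incidence objective and the *severe* event rate difference lack a window.

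**The case against.** A reader might infer that the trial's safety comparison as a whole is biased. The documents do not support that. The SAE endpoint stops at 30 days in both arms, months before any of the disputed SAE end dates. The safety hypothesis in Section 2.1 concerns rejection and dnDSA, and those outcomes have common windows. No test of any-AE incidence is planned. If *severe* in Section 13.4.3 is a slip for *serious*, the 30-day endpoint window applies and the ascertainment problem goes away for that analysis. Severe reactogenicity was only 1-2% in the transplant cohort cited in Section 5.2, so early clustering of severe events may be slight; at an assumed 2% the false-positive rate in the table is 6%. Longer watching after reduction is also a sensible design choice, because that is when harm from reduction may show. Section 8.3.3 says that blood-testing schedules are identical in both groups.

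Most of this stands, and it limits the point to the all-AE and *severe* AE comparisons. It does not remove it. Section 13.4.3 does not say that the 30-day window applies, and if *severe* means grade, nothing else supplies a window. Identical blood testing does not equalise AE collection rules. The conflict between Sections 12.2.1 and 12.4.1 is in the text whichever analysis is used.

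**Conclusion.** The point holds in limited form. AE collection is about 49 days against 30 for participants who complete reduction, and the reduction-arm SAE end dates differ by about 19 days between two sections. The one planned between-arm AE contrast has no window or denominator and names a different event set from the listed endpoint.

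The risk of bias is conditional. Proportions over the full windows would inflate the reduction arm (10% to about 16%, 20% to about 30%, assuming equal constant hazards). Person-time rates would understate it if events cluster after vaccine (0.65 and 0.72 of control in two assumed examples). Person-time with a constant hazard would show no bias. The SAE end-date conflict affects collection and descriptive tables, not the 30-day endpoint. The documents give no AE rates, so the actual size cannot be stated. The correction is worth making because it is cheap and removes a choice that could move the result in either direction.

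**What to change.** 1. In Section 13.4.3, make the between-arm AE comparison in one vaccine-anchored window common to both arms, for example Day 0-30, and state the denominator. The ratio of planned observation time is then 30/30 = 1.
2. Tabulate reduction-arm events from Day -5 to Day 0 and after Day 30 separately, so that harms of reduction stay visible to the DSMB and to readers.
3. State whether *severe* means a CTCAE grade (and which) or *serious*. In either case, specify the analysis of the listed 30-day serious-event endpoint explicitly.
4. Reconcile Sections 12.2.1, 12.2.3 and 12.4.1 and the event rows of Appendices 2 and 3. Give one SAE end date, anchored on the same day in both arms, with collection running at least to that date. State how long participants in each arm are asked to report AEs.

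The cost is protocol and SAP wording, plus a few more days of SAE collection in the reduction arm if the agreed date falls after the one in Section 12.4.1. The downside is that some reduction-arm events move from the formal comparison to a descriptive table.

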12.4.2 Collecting Adverse Events

Adverse events (including SAEs) may be discovered through any of these methods:

- Observing the subject.
- Interviewing the subject [e.g., using a checklist, structured questioning, diary, etc.].
- Receiving an unsolicited complaint from the subject.
- In addition, an abnormal value or result from a clinical or laboratory evaluation can also indicate an adverse event, as defined in Section 12.3, *Grading and Attribution of Adverse Events*.

12.4.3 Recording Adverse Events

Throughout the study, the investigator will record adverse events and serious adverse events as described previously (Section 12.2, *Definitions*) on the appropriate electronic case report form regardless of the relationship to study therapy regimen or study procedure.

Once recorded, an AE/SAE will be followed until it resolves with or without sequelae, or until the end of study participation, or until 30 days after the subject prematurely withdraws (without withdrawing consent)/or is withdrawn from the study, whichever occurs first.

12.5 Reporting of Serious Adverse Events and Adverse Events

12.5.1 Reporting of Serious Adverse Events to DAIT/NIAID

This section describes the responsibilities of the site investigator to report serious adverse events to the sponsor via the AE/SAE eCRF. Timely reporting of adverse events is required by 21 CFR and ICH E6 guidelines.

Site investigators will report all serious adverse events (see Section 12.2.3, *Serious Adverse Event*), regardless of relationship or expectedness within 24 hours of discovering the event.

For serious adverse events, all requested information on the AE/SAE eCRF provided. However, unavailable details of the event will not delay submission of the known information. As additional details become available, the AE/SAE eCRF will be updated and submitted. Initial SAE eCRFs should include as much information as possible, but at a minimum:

- AE term
- Relationship to study vaccination
- Relationship to study procedure
- Reason why the event is serious

- Supplementary eCRF pages that are current at the time of the SAE reporting e.g. medical history and vaccine administration

12.5.2 Reporting of Adverse Events to IRBs/IECs

All investigators shall report adverse events, including expedited reports, in a timely fashion to their respective IRBs/IECs in accordance with applicable regulations and guidelines.

12.5.3 Mandatory reporting to Vaccine Adverse Event Reporting System

Per the FDA EUA for the Moderna COVID-19 Vaccine and Pfizer-BioNTech COVID-19 Vaccine, reporting of the following to the Vaccine Adverse Event Reporting System (VAERS):

vaccine administration errors whether or not associated with an adverse event,
serious adverse events (irrespective of attribution to vaccination),
cases of myocarditis,
cases of pericarditis,
cases of Multisystem Inflammatory Syndrome in adults, and
cases of COVID-19 that result in hospitalization or death.

The site investigator, or designee, is also responsible for recording vaccination information in the state/local jurisdiction's Immunization Surveillance System or other designated system.

12.6 Reporting of Other Safety Information

An investigator shall promptly notify the site IRB as well as the SACCC when an "unanticipated problem involving risks to subjects or others" is identified, which is not otherwise reportable as an adverse event.

12.7 Review of Safety Information

12.7.1 Medical Monitor Review

The NIAID Medical Monitor shall receive monthly reports from the SACCC compiling new and accumulating information on AEs and SAEs recorded by the study site(s) on appropriate eCRFs.

In addition, the Medical Monitor shall review and make decisions on the disposition of the SAE and pregnancy reports received by the SACCC (See Sections 12.5.1, Reporting of Serious Adverse Events to Sponsor, and 12.6, Pregnancy Reporting).

12.7.2 DSMB Review

12.7.2.1 Planned DSMB Reviews

The Data and Safety Monitoring Board (DSMB) shall review safety data one month after all study participants have received study vaccine, unless a safety event requires earlier review. They will review the study again when the database is locked after the last patient's last visit. Interim DSMB reviews may occur at any time at the discretion of the medical monitor or the protocol chair. Data for the planned safety reviews will include, at a minimum, a listing of all reported AEs and SAEs.

12.7.2.2 Ad hoc DSMB Reviews

In addition to the pre-scheduled data reviews and planned safety monitoring, the DSMB may be called upon for *ad hoc* reviews. The DSMB will review any event that potentially impacts safety at the request of the protocol chair or DAIT/NIAID. In addition, the following events will trigger an *ad hoc* comprehensive DSMB Safety Review:

Any death that occurs in the study which is possibly or definitely related to study treatment regimen.

A Pausing Rule (outlined in Section 11.2) is met.

After review of the data, the DSMB will make recommendations regarding study conduct and/or continuation.

12.7.2.2.1 Temporary Suspension of enrollment for ad hoc DSMB Safety Review
See Section 11.2 for Participant Stopping Rules and Withdrawal Criteria

13. Statistical Considerations and Analytical Plan

13.1 Overview

This is a two-arm, open-label randomized trial with the goals of comparing efficacy of additional COVID-19 vaccine doses for solid organ transplant recipients with a prior weak immune response, with vs without immunoreduction. The study population will consist of solid organ transplant recipients who had a negative or low response to a licensed or authorized COVID-19 vaccine regimen, who otherwise meet inclusion criteria.

13.2 Endpoints/Outcomes

The primary endpoint is the proportional increase in antibody titer U/mL (using the Roche Elecsys® anti-RBD assay) at 30 days after the study dose of vaccine. Negative or very low antibody responses (<10 U/mL) will be imputed to 10 U/mL, to reduce the influence of measurement error on the proportional increase calculation among individuals with very low titers. Secondary safety endpoints include: local and systemic vaccine reactogenicity and/or allergy; serious adverse events occurring during the 30 days following the additional COVID-19 vaccine dose; treated acute cell-mediated and/or antibody-mediated allograft rejection (clinical or biopsy-proven) within 60 days following the COVID-19 vaccine dose; development of de novo donor-specific anti-HLA antibody within 90 days of the vaccine; graft loss within 60 days of the vaccine; and death within 60 days of the vaccine. Secondary efficacy endpoints include: SARS-CoV-2 PCR positivity; symptomatic COVID-19; COVID-19 requiring hospitalization; and longitudinal changes in SARS-CoV-2 antibody response during the study.

13.3 Measures to Minimize Bias

All participants will be randomized to receive immunoreduction or no immunoreduction prior to receipt of the vaccine. Randomization will be clustered by study site, and stratified by pre-dose titer (<50 vs ≥50 U/mL). Treatment group assignment will be unmasked to participants and clinical study staff. All laboratory staff will be masked to treatment assignment.

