1.3 Clinical Studies

The Moderna and Pfizer-BioNTech COVID-19 Vaccines are known to have excellent immunogenicity in the general adult population, even against some of the recently identified SARS-CoV-2 variants.^{27,28} These

vaccines are well-tolerated, with mostly mild-to-moderate local and systemic reactogenicity that is more pronounced after the second dose.^{29,30} However, organ transplant recipients have recently been shown to have much less reliable and robust responses to these vaccines.^{10,12} In a large (N=658) prospective cohort study of U.S. transplant recipients, only 15% of patients had a positive anti-SARS-CoV-2 S response after a first dose of either the Moderna or the Pfizer vaccine, with improvement to only 54% by four weeks after the second dose of vaccine. Patients who had a positive response after the first dose of vaccine had higher titers of anti-SARS-CoV-2 S after dose two as compared with those who had a negative or indeterminate response after dose one but did have a measurable response after dose two. In those with a positive anti-SARS-CoV-2 S response after dose two, antibody levels were substantially lower than in immunocompetent vaccine recipients. Associations with lack of vaccine response included older age, use of antimetabolite therapies, history of kidney transplantation (versus other organ transplant), more recent transplantation, and receipt of the Pfizer-BioNTech vaccine (versus the Moderna mRNA-1273 vaccine). In a study of 101 kidney transplant recipients maintained on belatacept-based immunosuppression, only 6% of patients had measurable anti-SARS-CoV-2 S after 2 doses of the Pfizer-BioNTech vaccine. In that study, SARS-CoV-2-specific T-cell responses by EliSpot were present in 30% of those tested (N=23) after two doses of vaccine.¹⁵

Several observational series and one randomized trial have evaluated antibody response to a third dose of SARS-CoV-2 vaccination in solid organ transplant (SOT) recipients, predominately following a third mRNA vaccination, using a variety of anti-spike antibody assays.⁴²⁻⁴⁶

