3.1 Description of Study Design

A randomized, open-label multi-site trial designed to induce an enhanced antibody response to SARS-CoV-2 in kidney and liver transplant recipients who have a negative or low (≤ 2500 U/mL) antibody response (using the Roche Elecsys® anti-SARS-CoV-2 S) following a completed primary series of mRNA COVID-19 vaccine. Participants will be randomized to receive a dose of COVID-19 vaccine (Moderna or Pfizer-BioNTech), with or without immunosuppression (IS) reduction.

[figure not shown]

Figure 1. Study Design Diagram

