4.4 Selection of Clinical Sites

This study will be conducted at approximately 15 clinical sites across the United States that have transplant programs with the population described in the protocol and which are able to comply with the requirements of the protocol. Sites may be added or withdrawn to meet the accrual goals outlined in the protocol.

5. Known and Potential Risks and Benefits to Participants

The risks cited below reflect the information currently included in the Moderna and Pfizer-BioNTech Package Inserts and Emergency Use Authorizations. The safety data accrued with the bivalent vaccines (Original and Omicron BA.1) and with the original COVID-19 vaccines are relevant to the updated 2023-2024 formulations because these vaccines are manufactured using the same process.

5.1 Risks of the Investigational Products as cited in the Full FDA EUA Prescribing Information

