5.7 Potential Benefits

There might be no benefit to participants in this study. If a participant achieves an increased level of antibody against SARS-CoV-2 as a result of participating in this study, there might be associated benefit. However, whether any participant will achieve this is unknown.

6. Investigational Agents

The study products used in this protocol are the: Moderna COVID-19 Vaccine and the Pfizer-BioNTech COVID-19 Vaccine. The doses provided for the study will be according to the current CDC and FDA Emergency Use Authorizations. The current available CDC recommended vaccines are provided to the clinical sites.

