13.4.2 Primary Analysis of Primary Endpoint(s)/Outcome(s)

The primary endpoint is a continuous measurement. All individuals whose primary endpoint is measured will be included in the analysis population.

For the comparison of immunoreduction vs no immunoreduction, we will reject the null hypothesis if the two-sided rank-sum p value comparing the -fold increase between the two groups falls below 0.05.

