Appendix 1: Screening (All Participants)

Initial Screening Assessment

• Chart review• Antibody consent• Anti-SARS-CoV-2 S (Roche Assay)
Final Screen

• Study consent form• Serum creatinine, eGFR (Kidney)• DSA (kidney only, sent to central lab, 90 day window)• Research blood (sent to central lab)• Hepatic panel, INR, direct bilirubin (liver)• Tacrolimus trough level• Pregnancy test (women of childbearing potential)
Randomization

1) Once the participant meets full eligibility, the participant may be randomized2) Once the participant is randomized, the appropriate appendix should be followed based on the group assignment:
○ Appendix 2: COVID-19 Vaccine Dose Alone 
OR
 
○ Appendix 3: IS Reduction plus COVID-19 Vaccine Dose

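### Section 13.3 says randomisation is clustered by site, which contradicts the participant-level design, test and power figure used everywhere else; the allocation scheme should be corrected and carried into the primary test

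*Combined protocol and SAP*

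**What the plan says.** Section 13.3 gives the scheme in one sentence: "Randomization will be clustered by study site, and stratified by pre-dose titer (<50 vs ≥50 U/mL". The sentence just before it has the participant as the unit: "All participants will be randomized to receive immunoreduction or no immunoreduction prior to receipt of the vaccine". Section 3.1 agrees: "Participants will be randomized to receive a dose of COVID-19 vaccine (Moderna or Pfizer-BioNTech), with or without immunosuppression (IS) reduction". Appendix 1 places allocation after individual screening, "Once the participant meets full eligibility, the participant may be randomized", and then sends each person to the schedule for their own group.

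Section 3.4 is the section headed for stratification and randomisation, but it says only that the study is open-label. No section defines *clustered*, gives a block scheme or names site as a stratum.

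The primary rule in Section 13.4.2 rejects the null if the "two-sided rank-sum p value comparing the -fold increase between the two groups falls below 0.05". It has no term for site or titre. Section 13.7 fixes 400 participants, 200 per group, and claims 80% power for a 20% difference in fold-increase, without an ICC or design effect. Section 4.4 sets the scale: "This study will be conducted at approximately 15 clinical sites across the United States".

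On product, Section 6 says "The current available CDC recommended vaccines are provided to the clinical sites", without saying how or when a participant's product is chosen. Sections 6.9 and 8.3.2 call the vaccine or dose assigned but do not describe the assignment.

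**The concern.** In trial usage, clustered randomisation means that the group, here the site, is allocated as one unit. If Section 13.3 meant that, about 15 sites rather than 400 people would be the randomised units, and every difference between sites in case mix or practice would be carried into the comparison of arms. The rank-sum test would treat correlated outcomes as independent and reject too often. The power figure would be too high.

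If individual randomisation was meant, the only sentence on the scheme is wrong, and a reader cannot tell whether site was a stratum, a blocking factor or neither. The choice of stratified analysis depends on that.

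Product is a lesser worry. Both manufacturers' vaccines are used, staff and participants know the arm, and people in the reduction arm know it by the Day -5 visit, before vaccination. Section 1.3 lists "receipt of the Pfizer-BioNTech vaccine (versus the Moderna mRNA-1273 vaccine" among the associations with a poor response. A product chosen after allocation could therefore differ between arms.

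**Working it through.** **1. The plan's own power figure.** Section 13.7 gives 200 per group, two-sided alpha 0.05, a rank-sum test, log-normal fold-changes and 80% power at a ratio of 3/2.5 = 1.2. It gives no SD, so the figure cannot be reproduced directly, but the SD it implies can be solved for. With the rank-sum efficiency 3/π = 0.955, the effective number per arm is 200 × 0.955 = 191, and

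SD = ln(1.2) / [(1.96 + 0.842) × √(2/191)] = 0.182 / (2.802 × 0.1023) = 0.636 on the natural-log scale.

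Simulating individually randomised, independent participants at SD 0.635 gave 80.8% power. The stated power therefore fits 400 independent people at about that SD, and leaves no room for a design effect.

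**2. The literal reading: whole sites allocated.** Mean site size is m = 400/15 = 26.7. The design effect is DE = 1 + (m − 1) × ICC, the effective sample size is 400/DE, and the actual level of a nominal 5% test is 2Φ(−1.96/√DE). The ICC is an assumption. For ICC 0.02: DE = 1 + 25.7 × 0.02 = 1.51, and the level is 2Φ(−1.96/1.23) = 0.111. The simulation column comes from 2,000 trials per row, using 15 sites and the unadjusted rank-sum test. The power column takes the SD from step 1 and assumes that the analysis allows for clustering.

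| ICC (assumed) | DE | Effective N | Level, formula | Level, simulated | Power, clustering allowed for |
|---|---|---|---|---|---|
| 0 | 1.00 | 400 | 0.050 | 0.0485 | 80% |
| 0.01 | 1.26 | 318 | 0.080 | 0.0770 | 71% |
| 0.02 | 1.51 | 264 | 0.111 | 0.1185 | 63% |
| 0.05 | 2.28 | 175 | 0.195 | 0.1855 | 46% |
| 0.10 | 3.57 | 112 | 0.299 | 0.2800 | 32% |

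**3. The participant-level reading.** The same simulation with individuals randomised within site gave levels of 0.0500, 0.0540, 0.0435, 0.0470 and 0.0375 for the five ICCs. Individual randomisation that ignored site gave 0.0490, 0.0495, 0.0495, 0.0415 and 0.0525. The simulation error is about √(0.05 × 0.95/2000) = 0.005. The planned test holds its level under either form.

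**4. Which reading fits the rest of the plan.** A titre below or above 50 U/mL belongs to a person and cannot stratify the allocation of whole sites that hold both kinds of participant. Appendix 1 randomises one person at a time once that person is eligible. A fixed 200 per group is natural for individual allocation, but with whole sites would depend on which sites fell in which arm. Only individual randomisation fits all of these.

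**The case against.** The strongest reply is that the inflation in step 2 belongs to a design that the rest of the plan excludes, and that it rests on an assumed ICC. This stands. A reader might infer from Section 13.3 that the trial is cluster-randomised and its p value invalid. The documents do not support that: Sections 3.1 and 13.3 and Appendix 1 all make the participant the unit, and under that reading the unstratified test is valid.

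A reader might also infer that, under individual randomisation, nothing balances the arms within site. That does not follow either. If the phrase means lists grouped or blocked by site, within-site balance is just what it provides. If site was ignored, chance imbalance between sites still does not bias the test.

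A third inference is that arm is confounded with product. No section says that a site holds only one product, and Sections 6.9 and 8.3.2 speak of an assigned vaccine or dose. Section 13.4.4 already plans to repeat the antibody analysis by product, and the association in Section 1.3 comes from a cohort given two doses of the earlier vaccines. What remains is that the timing of the product choice is not stated.

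Finally, Sections 6.1 to 6.4 list products no longer offered, so this is a late version and participants have probably been randomised already. A replacement sentence must describe what was done. That stands, and it shapes the fix. None of these replies removes the contradiction in the only sentence that states the scheme.

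**Conclusion.** The concern holds as an internal contradiction in a stated design rule. Section 13.3 names a scheme that cannot coexist with the unit of randomisation, the titre stratification, the primary test or the power figure, and Section 3.4 does not settle it. The likeliest explanation is a wording slip, and in that case the planned test has no type I error problem (simulated level 0.0375 to 0.054 for ICC 0 to 0.10).

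A level of about 8% to 20% is conditional on two things that the documents do not establish: that whole sites were allocated, and that the site ICC lies between 0.01 and 0.05. It also assumes about 15 sites of equal size. Product imbalance between arms is a possibility, not something the documents show.

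**What to change.** - **Scheme.** In Section 13.3, and repeated in Section 3.4, say that participants are individually randomised 1:1, stratified or blocked by site and by pre-dose titre (<50 vs ≥50 U/mL). If the scheme implemented differs, state that scheme instead. Had whole sites in fact been allocated, the analysis and power would have to be redone at site level, because the stratified test below needs both arms within each site.
- **Primary test.** Replace the unstratified rank-sum test in Section 13.4.2 with one stratified by the randomisation factors (van Elteren), by titre and site with small sites pooled. The unstratified test holds its level, so this is not a repair of validity: it makes the analysis match the allocation. Write the pooling rule down before arms are compared.
- **Product.** For participants still to be randomised, record the intended product before allocation is released. This cannot help those already randomised; for them the product analysis in Section 13.4.4 remains.

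The cost is a corrected sentence in two places, one data field and a stratified version of the planned test. Fifteen sites and two titre strata make 30 cells averaging 400/30 = 13.3 participants, so some blocks will be incomplete, arm sizes may differ slightly, and sparse strata will need pooling. Sample size and endpoint do not change.
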